Patients will be referred by the Spectrum Health breast surgeons. If the patient is interested, the investigator or research staff will provide a copy of the informed consent for the patient to review. Spectrum Health research staff will then follow up with the patients to further discuss the study and confirm that the patient is interested in participation.

Patients will then be consented by a clinical research coordinator. Typically, this would occur at the hospital where they will be undergoing their surgery. The coordinator will review the consent with the patient (and family or significant other, as applicable) and have the patient sign it. The coordinator will make all reasonable attempts to keep the discussion as private as possible. In order to minimize coercion, it will be made very clear to patients that their participation is strictly voluntary and that not choosing to participate will in no way affect their present or future care at Spectrum Health.

Once the patient has been randomized to either PEC or PVB, the anesthesiologist on call for local blocks will see the patient and review that analgesic plan and the risks of that specific procedure with the patient. This meeting and explanation are standard, but they may also answer questions the patient may have related to the study.

We anticipate enrolling 128 total patients in the study, 64 in the PVB arm and 64 in the PEC arm.

There will be no payment to patients for inclusion in the study.

b. Inclusion and Exclusion Criteria

Inclusion Criteria:

- i. Female patients \geq 18 years of age
- ii. Total mastectomy or partial mastectomy with or without reconstruction OR planned lumpectomy.
- iii. Patient determined by their surgeon as medically able to receive a regional block for post-operative analgesia
- iv. Patient agrees to participate in the study and signs informed consent

Exclusion Criteria:

- i. Neoadjuvant radiation therapy
- ii. Stage IV cancer
- iii. Planned general anesthesia use during surgery
- iv. Allergies to ropivacaine, midazolam, fentanyl, or propofol
- v. Pregnant women
- vi. Prisoners
- vii. Adults unable to consent
- viii. Non-English-speaking patients

c. Study Endpoints

Primary Outcome Variables:

Intraoperative narcotic use, Post Anesthesia Care Unit (PACU) narcotic use and postoperative narcotic use. We would expect that all variables will have a lower values in patients randomized to PEC versus PVB.

Secondary Outcome Variable(s):

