- vii. Total of extra narcotic and sedative medication used while in PACU and in the first 24 hours post-PACU (or until discharge, whichever comes first)
- viii. Total doses of anti-nausea medication used while in PACU and in the first 24 hours post-PACU (or until discharge, whichever comes first).
- ix. Which anesthesiologist performed the procedure
- x. Two-week post-operative visit pain rating (subjective information from the patient about their over-all pain rating for the previous two weeks, as well as the approximate last time they used pain pills)
- xi. Number of phone calls to the surgeon's office for concerns about pain in the time post-discharge and prior to the office visit.

¹Include distance the patient lives from the Lemmen-Holton Cancer Pavilion, their self-reported ethnicity and age.

²Include stage of tumor, outpatient chronic use of narcotics, diagnosis of chronic pain, ASA classification, current diagnosis, major comorbidities and BMI.

³Defined as total amount of narcotic/sedative medication given during surgery, in milligrams,

Standard of care follow-up will occur at 2 weeks with the physician who performed the surgery. Patient will be asked about pain pill use; those units will be converted to morphine equivalents. This information may also be obtained through a phone call.

This trial is registered on clinicaltrials.gov

Schedule of Events:

Study Requirements	Pre-Surgery Visit	Day of Surgery	PACU	1 st 24 hrs. post-surgery	Post-Surgery Visit (2 wks after surgery, +/- 1 week) ³
--------------------	-------------------	----------------	------	--------------------------------------	---

Eligibility Criteria	X				
Consent	X¹	X			
Randomization		X			
Surgery, using PEC or PVB		X			
Data Collection ²		X	X	X	X
Adverse Events		X	X	X	X

¹ Consent may be done either prior to the day of surgery or on the day of surgery, depending on timing and patient preference.

² Includes patient demographics, medical history, block procedure used (PVB or PEC), method of pain control used during surgery, extra narcotic/sedative use during surgery, length of surgery, extra narcotic and sedative use in PACU, name/total dosage of narcotic use during post-op hospitalization, duration of hospitalization

³ Data collected from this time period may be done over the phone as well as at the surgeon's office.

e. Data Management

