Data to be collected are detailed in Appendix B (pdfs of REDCap database for this study). Data will be managed by Spectrum Health research staff and kept in a locked cabinet or a limited-access electronic drive.

f. Provisions to Monitor the Data for the Safety of Subjects

The Principal Investigator will oversee the safety of the study. This safety monitoring will include careful assessment and appropriate reporting of adverse events (see "Adverse Events" below).

g. Withdrawal of Subjects

A patient may be withdrawn from the study prior to the expected completion of that subject for failure to adhere to protocol requirements. Patients may choose to withdraw from the study at any time. Data that have already been collected on these patients will still be used.

The primary investigator may remove a patient at any time from this research study if it is felt to be in the best interest of the patient.

9. Statistical Plan:

a. Sample Size Determination

The primary outcome variable for this study is the difference in narcotic use between the PEC group and the PVB group during the first 24 hours following surgery. If we define a clinically important effect as the mean narcotic use in the PVB group is twice that seen for the PEC group, with a standard deviation equal to the mean of the PVB group, with $\alpha=0.05$ and $\beta=0.20$, we will be able to detect a statistically significant difference with 64 subjects in each group, using the unpaired t-test. Complication rates will also be compared between the two

groups, although with an anticipated rate of only 5% in the PVB group, it is unlikely with the projected sample size that we will find a statistically significant effect for this variable.

b. Statistical Methods

Summary statistics will be calculated. Quantitative data will be expressed as the mean + SD, while nominal data will be expressed as a percentage. Comparisons between groups for quantitative variables will be performed using the t-test. Nominal variables will be evaluated using the Chi-Square test. The data will be analyzed as intention to treat. Significance will be assessed at $p<0.05$.

10. Risks to Subjects:

Risks of both procedures are very low – less than 5% for each risk listed here.

PEC

- a. Vascular puncture
- b. Inadequate analgesia
- c. Intraneuronal injection, resulting in transient neuropathy
- d. Incomplete nerve block
- e. Infection

PVB

- a. Pneumothorax
- b. Vascular puncture
- c. Incomplete nerve block

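### Study Endpoints lists three primary outcomes, but Section 9a names and powers only one, and Section 9b gives no rule for handling several primaries

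*Combined protocol and SAP*

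**What the plan says.** Under its plural heading for primary outcomes, the Study Endpoints section lists "Intraoperative narcotic use, Post Anesthesia Care Unit (PACU) narcotic use and postoperative narcotic use". It adds: "We would expect that all variables will have a lower values in patients randomized to PEC versus PVB".

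Section 9a (Sample Size Determination) uses the singular: "The primary outcome variable for this study is the difference in narcotic use between the PEC group and the PVB group", measured "during the first 24 hours following surgery". The effect size, SD, alpha, beta, sample size and test that follow all belong to that one variable.

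Section 9b (Statistical Methods) prescribes t-tests for quantitative variables and Chi-Square tests for nominal ones. It then says "Significance will be assessed at" p<0.05. It names no primary variable and gives no multiplicity adjustment, testing order or success rule.

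The time window is also described in more than one way. Section 9a counts from surgery, and a Schedule of Events column is headed "1 st 24 hrs. post-surgery", next to a separate PACU column. Data item vii, under Procedures Involved in the Research, instead collects "Total of extra narcotic and sedative medication used while in PACU and in the first 24 hours post-PACU (or until discharge, whichever comes first".

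**The concern.** A reader looking for the primary outcome would normally go to the endpoints section, and there finds three. A reader starting from the statistical plan finds one. The Section 9a variable is not clearly any of the three. It starts after surgery, so it leaves out intraoperative use, and the documents do not settle whether it includes PACU use.

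This matters most if the measures disagree, for example if PACU use differs significantly between arms and 24-hour use does not. The Study Endpoints section would allow one headline and Section 9a another, and nothing written in advance chooses between them. If the choice is made after the data are seen, the 5% error rate is no longer protected.

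**Working it through.** **Inputs from Section 9a.** The PVB mean is M, the PEC mean is M/2 and the SD is M. Alpha is 0.05, beta is 0.20, and there are 64 per arm with an unpaired t-test. Sidedness is not stated.

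**Reproducing the plan's figure.** The standardised effect is d = (M − M/2)/M = 0.5. For a two-sample t-test at two-sided 0.05 with 80% power, n = 63.77 per arm, which rounds up to 64. Power at 64 per arm is 80.1%. A one-sided test would need about 51 per arm (50.15 rounded up), so the plan used a two-sided test. The sample size is correct for one outcome.

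**Assumptions for three primaries.** The documents give no success rule, no correlation between the outcomes, and no effect size for intraoperative or PACU use. The figures below take an equal correlation r between each pair of outcomes, from 0 to 0.9. Where power is involved, they take d = 0.5 on all three. Narcotic measures in the same patients are unlikely to be uncorrelated, so r = 0 is an extreme.

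**Rule A: any one of three at 0.05 counts as success.** With no true difference and r = 0, the false-positive rate is 1 − 0.95³ = 0.143. For r > 0 it is the probability that at least one of three correlated standard normal statistics exceeds 1.96 in absolute value.

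**Rule B: all three must reach 0.05.** At r = 0, power is 0.8015³ = 0.515. For r > 0 it comes from simulated t-tests (40,000 trials, 64 per arm). The error rate is not inflated under this rule.

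| r | Rule A: two-sided false-positive rate | Rule B: power | Only one or two of three significant |
|---|---|---|---|
| 0 | 14.3% | about 51% | about 47% |
| 0.5 | 12.5% | about 61% | about 34% |
| 0.7 | 10.9% | about 66% | about 27% |
| 0.9 | 8.4% | about 72% | about 15% |

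The last column uses the same assumption of d = 0.5 on every outcome. It shows how often a split result would arise even if all three effects were real and equal.

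**Possible remedies at 64 per arm.**
- With the Section 9a variable as sole primary, or first in a fixed sequence, alpha is 5% and power for that outcome is 80.1%.
- With Bonferroni over three outcomes (0.05/3 = 0.0167 each), alpha is controlled but power for any single outcome with d = 0.5, including the 24-hour one, falls to 65.6%. Restoring 80% would take 86 per arm.

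**The case against.** The strongest reply is that Section 9a already settles the matter. It speaks of the primary outcome in the singular and ties every design figure to it. On that reading there is one primary, alpha and power are as stated, and the endpoints list is only poorly aligned with the statistical section. This is the more natural reading of Section 9a, and what stands of it is that the stated alpha and beta do hold for that variable. But nothing in the documents says that Section 9a overrides the Study Endpoints section, so the conflict remains.

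A second reply is that the losses in the table come from rules the plan never adopts. That is correct. A reader might infer that this trial has a false-positive rate of 14%, or power of only about half. The documents do not support either statement, because both are conditional on a rule, correlations and (for power) effect sizes that the plan does not give. The two rules also fail in opposite directions. Nor is the sentence expecting lower values on all variables with PEC a requirement that all three succeed: it predicts a direction.

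A third reply is that the first 24 hours after surgery plainly include PACU, and that a schedule column heading does not define an endpoint. This has some force. It does not remove the ambiguity, because Study Endpoints lists PACU and postoperative use separately and data item vii starts its 24 hours after PACU.

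A reader might also infer that the plan would pool narcotics with sedatives, or lacks a common unit for the primary. The documents do not establish this. "Patient will be asked about pain pill use; those units will be converted to morphine equivalents" concerns pain pill use asked about at the two-week follow-up, and a footnote to the Schedule of Events already lists narcotic name and total dosage during the postoperative stay.

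**Conclusion.** The point stands, and it should be corrected before analysis. The plan defines its primary outcome in two incompatible ways, and its stated alpha and power belong to only one of them. That conclusion rests on the text alone.

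The size of the consequence is conditional. Over correlations of 0 to 0.9, an any-one rule would put the two-sided false-positive rate at about 14% to 8% instead of 5%. An all-three rule would put power at about 51% to 72% instead of 80%, if d = 0.5 held for every outcome. At every correlation examined, neither rule delivers both stated figures. If Section 9a governs, both are delivered.

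The differing time windows are a lesser part of the same problem: even a reader who accepts Section 9a cannot tell exactly which quantity is tested.

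Whether a superiority test can answer the Section 4 objective of equal analgesia is a separate question and is not decided here.

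**What to change.** In Study Endpoints, make the Section 9a variable the sole primary outcome. Move the other narcotic measures to secondary outcomes, reported with 95% confidence intervals and not used to declare success. Alternatively, keep them in a stated fixed sequence, each tested at 0.05 only if the 24-hour outcome and every earlier step is significant. Say in Section 9b which of these applies.

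In the same edit, give the primary one time window. Reconcile Section 9a and the Schedule of Events column with data item vii, say whether PACU use is included, and say how use is counted for patients discharged before the window ends.

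The cost is text in Study Endpoints, Sections 9a and 9b, and data item vii. The sample size stays at 64 per arm, with 80.1% power for the primary under the Section 9a assumptions. The downside is that success can no longer be claimed on intraoperative or PACU use alone.

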Length of operation, estimated blood loss, incidence of postoperative nausea, subjective pain at two weeks (including patient's overall pain rating for the previous two weeks, the patient's stated last time they used pain pills) and number of calls to physician's office following hospital discharge.

d. Procedures Involved in the Research

This is a prospective, randomized study.

Following satisfaction of the inclusion/exclusion criteria and signed informed consent, patients will be randomized to paravertebral block or a pectoral nerve block. The randomization schedule will be set-up prior to study start using an Excel spreadsheet. Spectrum Health statisticians designed the randomization schedule to meet significance for the endpoints. Randomization is 1:1, PEC:PVB. If the patient is unwilling to be randomized to one or the other type of block, they will not be able to participate in the study. After each patient is consented, the randomization schedule will be checked and the data sheet with the type of block to be used will be placed in

the patient chart. The research coordinator will notify anesthesia of which block will be used on the patient.

Patients will proceed to surgery per usual standard of care. The PVB is performed along the spine utilizing ultrasound guided technique. The PEC is performed anteriorly, at the level of the axillary line, also utilizing ultrasound guided technique. Each block will be performed using 20-30 mL 0.5% Ropivacaine¹ per side. Midazolam and fentanyl will be used for sedation as needed. Intraoperatively, patients will undergo monitored anesthesia care with a propofol infusion (50-150 mcg/kg/min). Additional IV fentanyl will be given as needed. Anesthesia will be converted to general anesthesia if the patient is unable to tolerate the procedure with sedation and block anesthetic or if general anesthesia is preferred by the surgeon. This will not disqualify the patient, but the conversion will be noted in REDCap.

¹Package inserts for these FDA-approved drugs are included as Appendix A to the protocol.

All post-operative care will be standard of care.

Data collected will include the following:

- i. Demographics¹
- ii. Medical history²
- iii. Surgical procedure performed & pain control technique(s) used
- iv. Extra doses of narcotic and sedative medication used during surgery.³
- v. Length of surgery
- vi. Duration of hospital stay (measured in minutes)

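### Two secondary outcomes taken at a contact on any day from 7 to 21 need a rule for patients still using pain pills and a pain question tied to fixed postoperative days; the t-test provides neither

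*Combined protocol and SAP*

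**What the plan says.** - Study Endpoints names as secondary outcomes "subjective pain at two weeks (including patient's overall pain rating for the previous two weeks, the patient's stated last time they used pain pills".
- Procedures Involved in the Research, data item x, defines the two-week information as the patient's "over-all pain rating for the previous two weeks", "as well as the approximate last time they used pain pills".
- The Schedule of Events places this contact at "2 wks after surgery, +/- 1 week". Its footnote adds: "Data collected from this time period may be done over the phone as well as at the surgeon's office".
- Section 9b, Statistical Methods, states: "Comparisons between groups for quantitative variables will be performed using the t-test". Nominal variables go to the chi-square test. No time-to-event method, rule for patients still taking pills, or adjustment for day of contact appears.
- Data Management refers to Appendix B for the REDCap forms. Those forms are not in the text reviewed, so the coding of the last-use item cannot be seen.

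**The concern.** A patient who is still taking pills when contacted has no last-use time yet. All that is known is that it lies beyond the contact day. Such patients are to be expected: contact may come as early as one week after surgery, the operations run from lumpectomy to mastectomy with reconstruction, and chronic narcotic use is recorded as history but is not an exclusion.

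If the item is treated as a number of days, the plan sends it to a t-test, which cannot use a censored value. The analyst must enter the contact day as if use had stopped then, or set the value to missing. Either choice pulls the two arms together.

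The pain rating has a separate difficulty. Its look-back has a fixed length but is counted from the contact and not from surgery, so it covers different postoperative days in different patients.

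At stake are the size and meaning of two secondary comparisons, not the primary one.

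**Working it through.** **1. The plan's own figure.** The only sample size is for 24-hour narcotic use (section 9a). The difference is half the PVB mean and the SD equals the PVB mean, so the standardised difference is 0.5. The normal formula gives 2 × (1.960 + 0.842)² / 0.5² = 62.8, or 63 per group. The exact two-sided t-test gives 63.77, or 64, with power 0.801. The stated 64 is reproduced. No figure is given for the two-week items.

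**2. Window and look-back.** 14 − 7 = day 7 and 14 + 7 = day 21. A 14-day look-back then covers:

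| Contact | Postoperative days covered | Preoperative days included | Early postoperative days missed |
|---|---|---|---|
| Day 7 | 0–7 | 7 | 0 |
| Day 14 | 0–14 | 0 | 0 |
| Day 21 | 7–21 | 0 | 7 |

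The first and last rows share essentially no postoperative days.

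**3. Assumptions for last use.** The documents give no distribution of pill use or contact day. Assumed here: exponential time T to last use with mean m, and contact C uniform on days 7 to 21, alike in both arms. Three pairs of means are used: 7/5, 10/7 and 14/9 days.

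**4. Share still using at contact.** p(m) = (m/14)(e^(−7/m) − e^(−21/m)).
- m = 5: (5/14)(0.2466 − 0.0150) = 0.083
- m = 7: (7/14)(0.3679 − 0.0498) = 0.159
- m = 9: (9/14)(0.4594 − 0.0970) = 0.233
- m = 10: (10/14)(0.4966 − 0.1225) = 0.267
- m = 14: (14/14)(0.6065 − 0.2231) = 0.383

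**5. Differences in mean days.**
- Contact day taken as last use: the arm mean is m(1 − p). For 7/5 this is 5.887 − 4.586 = 1.30; for 10/7, 7.328 − 5.887 = 1.44; for 14/9, 8.632 − 6.903 = 1.73.
- Ongoing users dropped: the arm mean is E[T | T ≤ C].
- Everyone contacted on day 14: m(1 − e^(−14/m)).
- The most Kaplan-Meier could recover, the restricted mean to day 21: m(1 − e^(−21/m)). This gives 6.651 − 4.925 = 1.73; 8.775 − 6.651 = 2.12; 10.876 − 8.127 = 2.75.

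| Means | Contact day as last use | Ongoing users dropped | All contacted day 14 | Restricted mean to day 21 | Unrestricted |
|---|---|---|---|---|---|
| 7/5 | 1.30 | 0.77 | 1.36 | 1.73 | 2 |
| 10/7 | 1.44 | 0.70 | 1.48 | 2.12 | 3 |
| 14/9 | 1.73 | 0.73 | 1.75 | 2.75 | 5 |

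**6. Power and type I error** (simulation, 64 per arm, 4,000 trials, contact day as last use for the t-test).
- Power, t-test then log-rank: 0.387 and 0.418 (7/5); 0.375 and 0.414 (10/7); 0.468 and 0.549 (14/9). The gains are 3.1, 3.9 and 8.1 points. Across repeat runs they lay between about 3 and 9.
- With no true difference and the same contact timing in both arms, the t-test rejects in 0.046 to 0.051 of trials.
- In a deliberately extreme case, one arm contacted on days 7–14 and the other on days 14–21, the t-test rejects in 0.06, 0.22, 0.51 and 0.81 of trials for means of 4, 7, 10 and 14 days. Log-rank stays near 0.05.

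**The case against.** The strongest reply has four parts.

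**Coding.** A reader might infer that the protocol treats ongoing users as having stopped. It does not say so. It lists "stated last time they used pain pills" within subjective pain at two weeks and does not state whether the item is a date, a duration or a category. The forms may already hold a still-using option. This stands, and the point is therefore conditional on last use being analysed as a time. A category would not settle the matter: it would go to the chi-square test, and the proportion still using depends on the day of contact.

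**Size.** A reader might set 1.30, 1.44 and 1.73 days against 2, 3 and 5 and blame the wide window and the t-test for the whole gap. The working does not support that. With everyone contacted on day 14 the differences are nearly the same (1.36, 1.48 and 1.75), so most of the shrinkage comes from short follow-up. No analysis of data ending on day 21 could recover 2, 3 and 5.

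**Consequence.** A reader might also infer that the trial is tilted towards finding the blocks equal. Equal analgesia is the stated objective, but Study Endpoints expects lower narcotic use with PEC, and section 9a powers the trial for a difference in 24-hour use. These two items do not enter that comparison. With the same contact timing in both arms, type I error is preserved. Nothing in the documents suggests that timing differs by arm, although nothing guards against it.

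**Recall.** At the nominal visit, the previous two weeks are the two weeks since surgery, and the protocol says follow-up occurs at 2 weeks. The mismatch arises only away from day 14, and uniform contact is a pessimistic assumption. That is fair, but the schedule permits the full window and allows contact by telephone.

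**Conclusion.** The point holds as a minor one. The contact window, the t-test as the only method for quantitative variables, and the shifting look-back are all in the text. If last use is analysed as a time, censoring is ignored. Under the assumed exponential times and uniform contact, the estimate is about 1.3, 1.4 and 1.7 days where 1.7, 2.1 and 2.7 could be recovered to day 21, and about 0.7 to 0.8 if ongoing users are dropped. The power lost against log-rank is about 3 to 9 points. These sizes are illustrative, since every distributional input is assumed.

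The look-back mismatch needs no assumption beyond the permitted window. The documents do not support reading this as a flaw in the primary comparison, as inflated type I error when contact timing is the same in both arms, or as proof of how ongoing users are coded.

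**What to change.** 1. On the two-week form, record the contact date and a yes/no item for whether the patient is still taking pain pills. If the forms in Appendix B already hold these, say so in section 9b.
2. In section 9b, analyse time from surgery to last pain-pill use by Kaplan-Meier and log-rank, with ongoing users censored at the contact date. Because log-rank gives no difference in days, a restricted mean difference over a horizon fixed in advance may be added. The horizon should stop while enough patients remain under observation: few will be followed to day 21, and a day-14 horizon would give a difference close to the naive one, though with a clear meaning.
3. Anchor the pain question to a fixed postoperative period that every contact covers, such as the first 7 days.

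The cost is one extra item, the contact date if it is not already captured, a reworded question and a standard analysis. Late contacts would have somewhat longer recall, and the pain rating would no longer cover the second week. The primary outcome and the 64 per group do not change.

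### The primary outcomes are narcotic use, but the data items behind them are worded as narcotic-and-sedative totals, and no opioid scale is stated for surgery, PACU or the first 24 hours

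*Combined protocol and SAP*

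**What the plan says.** Section 8c (Study Endpoints) lists narcotic use during surgery, in PACU and postoperatively as the primary outcomes. Section 9a (Sample Size Determination) bases the calculation on narcotic use in the first 24 hours after surgery. Neither gives a unit.

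The data items in Section 8d are worded differently:

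- **Surgery.** Item iv is "Extra doses of narcotic and sedative medication used during surgery". Its footnote 3 defines this as "total amount of narcotic/sedative medication given during surgery, in milligrams".
- **PACU and first 24 hours.** Item vii is "Total of extra narcotic and sedative medication used while in PACU and in the first 24 hours post-PACU", with no unit.
- **Schedule of Events, footnote 2.** For surgery it has "extra narcotic/sedative use during surgery", and PACU again combines the two classes. For the hospital stay after surgery it lists narcotics alone: "name/total dosage of narcotic use during post-op hospitalization".
- **Two-week follow-up.** Patients are asked about pain pills, and "those units will be converted to morphine equivalents". No other opioid conversion appears in the text.

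Section 9b compares quantitative variables by t-test and gives no derivation rule. On the drugs themselves, Section 8d names fentanyl, midazolam and propofol for sedation and surgery. After that, "All post-operative care will be standard of care". The history items include "outpatient chronic use of narcotics", and chronic use is not an exclusion.

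**The concern.** Section 9a expresses its effect as a ratio of mean narcotic use and tests it with an unpaired t-test, so each patient needs one number on one scale. The stated measurement rules do not produce that number.

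Two separate problems follow. First, if footnote 3 is applied as a single sum, the intraoperative figure is almost entirely sedative and says little about narcotic use. Second, even if sedatives are kept apart, the plan does not say how different opioids are to be added in PACU or over the first 24 hours, and the protocol does not fix which opioids are used after surgery. That second gap touches the variable behind the sample size. A conversion left open in the plan could be chosen after the data are seen, and the t-test result could depend on it.

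**Working it through.** **1. The plan's own figure.** Section 9a sets the PVB mean at twice the PEC mean and the SD equal to the PVB mean. With the PVB mean as the unit, the difference is 0.5 and the SD is 1, so d = 0.5/1 = 0.5. For a two-sided alpha of 0.05 and 80% power, the t-test needs 63.77, so 64 per group; power at 64 is 80.1%. The stated figure reproduces. Because d is built from ratios, it is the same on any single opioid scale.

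**2. Surgery, if the drugs are added as one milligram sum.** The propofol rate of 50-150 mcg/kg/min is from Section 8d; weight, duration and fentanyl dose are assumptions.

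Propofol (mg) = rate x weight x minutes / 1000.

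- 70 kg, 90 min: 50 x 70 x 90/1000 = 315 mg, to 150 x 70 x 90/1000 = 945 mg.
- Lowest corner (50 kg, 30 min): 50 x 50 x 30/1000 = 75 mg.
- Highest corner (100 kg, 180 min): 150 x 100 x 180/1000 = 2,700 mg.

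With 0.05-0.4 mg of fentanyl, the narcotic share of the sum runs from 0.05/2,700.05 = 0.002% to 0.4/75.4 = 0.53%.

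**3. What that does to a comparison (illustration only).** Borrow Section 9a's effect for surgery. Let D be the fentanyl difference (half the PVB mean), so that the fentanyl SD is 2D. Let s be the SD of the sedative amount, assumed independent of fentanyl and equal in both arms. Then d = D / sqrt((2D)^2 + s^2), with 64 per group:

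| Sedative SD s (assumed) | D = 0.05 mg | D = 0.1 mg | D = 0.2 mg |
|---|---|---|---|
| 0 (fentanyl alone) | 80.1% | 80.1% | 80.1% |
| 0.5 mg (midazolam only) | 8.5% | 18.1% | 41.8% |
| 1 mg (midazolam only) | 5.9% | 8.5% | 18.1% |
| 25 mg or more (propofol) | 5.0% | 5.0% | 5.0% |

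Without assumed doses, let the sedative SD be k times the PVB narcotic mean. Then d = 0.5/sqrt(1 + k^2), and power is 71% at k = 0.5, 51% at k = 1, 24% at k = 2 and 8.5% at k = 5.

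**4. Surgery, if the classes are totalled separately.** None of the loss in step 3 occurs. Fentanyl is the only narcotic named for this phase, so milligrams of fentanyl would be close to a usable measure.

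**5. PACU and first 24 hours.** Item vii combines the classes with no unit. Schedule footnote 2 separates narcotics for the hospital stay by name and total dosage, so a narcotics-only total can be derived there, but no rule for adding different opioids is given. The documents do not state the postoperative drug mix, so no numerical effect can be computed.

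**The case against.** The best reply is that the documents never say the two classes will be summed for analysis. Wherever the outcome itself is named, it is narcotic use. Footnote 3 defines a data item, its slash allows one total per class, and it ends in a comma, so words may be missing. Section 8e refers to Appendix B for the data fields; that appendix was not available and may record each drug separately. All of this stands.

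A reader might infer that the trial will test a pooled milligram sum, and so has about 5% power for the intraoperative outcome. The documents do not support that. The figure needs the pooled reading, a 24-hour effect moved to surgery, assumed SDs, and sedative use that is equal between arms and independent of narcotic use. A weaker block could raise both classes. If a dominant sedative itself differed by d = 0.5, power for the sum would be about 80%, although the test would then be measuring sedative. Item iv also speaks of extra doses while its footnote speaks of the total, so it is unclear whether the planned propofol infusion counts at all.

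The two-week morphine equivalents might also be meant to feed postoperative narcotic use, since Section 8c sets no time limit there. That is possible, but the sentence covers pills reported at follow-up and gives no scale for surgery, PACU or the 24-hour variable in Section 9a.

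Finally, doses recorded by drug can be converted later without loss, and one table would apply equally to both arms. That limits the damage to the data. It does not supply a rule fixed in advance.

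**Conclusion.** The point holds as a gap in the definition of the primary outcome, and it should be fixed. Taken literally, the stated totals do not measure narcotic use: sedative milligrams would swamp fentanyl in surgery, and unlike opioids would be added by weight afterwards. The visible text states no conversion for any of the three primary periods.

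The size is limited. The sample size of 64 per group is correct on its own inputs and does not change. The power figures only illustrate the literal pooled reading; with totals by class there is no such loss in surgery. For PACU and the first 24 hours, the effect cannot be quantified from the documents. Nor do the documents show that narcotic data will be inseparable: schedule footnote 2 points the other way for the hospital stay, and Appendix B may do so for the rest. Confidence is medium, because it depends on fields that were not available.

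**What to change.** - In footnote 3, item vii and Sections 8c and 9a, define narcotic use in each period (surgery, PACU, first 24 hours) as opioids only, recorded by drug, dose and route.
- Convert to morphine equivalents with one table named before analysis, as is already planned for the two-week pills, and sum within each period.
- Report sedatives separately, by drug.
- Align item vii with schedule footnote 2, so that both describe postoperative narcotics by name and total dosage, and check that the Appendix B fields match.

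The cost is a wording change, one conversion table, and minor extra abstraction by drug for surgery and PACU. The downside is that results will depend somewhat on the table chosen, which is a reason to fix it in advance. The sample size stays at 64 per group.
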